
1b. Patient Usability (patient perspective): We will also conduct a focus group with the initial 10 patients enrolled in the intervention arm of the study to obtain user feedback regarding any barriers to implementation or usability suggestions to further adapt the intervention if necessary before additional participants are enrolled. The qualitative methods detailed above will be employed. The patient focus group will take approximately two hours and will be conducted in a confidential conference room at NUMC. Patient participants will be compensated \$50 for their participation. The discussion guide for the patient focus group will be developed by the Drs. [name] and [name] with input from the CAB (see Appendix 2). Discussion topics include (but are not limited to) the following: 1) patients' perceptions of the ease of the study implementation (using the equipment, uploading) 2) patients' perceptions of usefulness of the intervention; 3)

patients' input on barriers/challenges to intervention implementation; and 4) suggestions for improvements and/or adjustments that should be made. Data will be coded and analyzed using NVivo (see above) to identify the barriers and challenges that need to be addressed as study implementation continues in order to ensure a high level of usability.

Patient Utilization: This phase of intervention development will also involve an ongoing process evaluation of usability using quantitative methodology. Again, this is so that adjustments can be made, as necessary, as the TSM intervention is implemented.

We will operationalize usability using the following measures:

- 1) Rate of acceptability
- 2) Rate of installation acceptance
- 3) Upload compliance
- 4) Total number of visits
- 5) Patient satisfaction

Aim 2: we propose to conduct the first randomized controlled trial to telemonitor minority community-dwelling patients with CHF (NYHA class1-3) for 3 months after hospital discharge or CHF. We will compare hospital and emergency room utilization, as well as QoL, between TSM and standard of care groups.

This is a prospective randomized controlled trial of 104 community-dwelling patients from disparity communities living with CHF 18 years and older.

In this study, patients will be randomized either to TSM or to standard of care once they have given consent to participate to *directly compare TSM to standard of care* in a health disparity population.

Table 1. Proposed Intervention: TSM and Standard of Care (SOC)		

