Upload compliance: We are arbitrarily defining three levels of compliance: High, moderate and minimal. "Minimal" compliance is defined as at least one upload per week for 6 out of the 12 weeks. "Moderate" compliance is defined as at least one upload per week for 9 out of the 12 weeks, and "High" compliance is defined as at least three uploads per week for 9 out of the 12 weeks. *A secondary compliance measure will be the number of uploads over* the 90 day period. = u/d. (maximum number of possible uploads = 90). All of these measures will be appropriately prorated for patients who die, or are hospitalized during the study, and are therefore not subject to uploading requirement during those times. With a sample size of 52 patients, the rates of compliance can be estimated to, at worst, +- 13.9%, with a 95% CI.

Total number of visits: We will compute the proportion of 12 scheduled visits that are kept. Therefore, if a patient is being followed for *w* weeks, there should be *w* scheduled visits. If the number scheduled visits that are kept is denoted by *v*, then the proportion of scheduled visits kept = v/w. Visit participation rates will be averaged across patients, and the mean rate will be computed, along with 95% confidence intervals. There is a maximum of 12 possible telehealth visits over the 3 month study period.

Patient satisfaction: We will measure patient perceptions of usability using a slightly modified version of the Telemedicine Satisfaction and Usefulness Questionnaire (Appendix 3). This 22-item questionnaire, which utilizes a 5 point Likert scale, will elicit a total sum score of satisfaction/usability that will then be dichotomized into satisfied vs. not satisfied based on previous literature.

Sample size considerations: We will randomize 116 patients as they are discharged from the hospital (58 per arm) in order to yield a maximum of 52 patients in the TSM arm of the study over a two year period.

These scores will be assessed using mean scores, percentages and histograms.²⁵ For satisfaction rates of 50%, 75% and 90%, with a sample size of 52, the corresponding 95% confidence intervals will have precision of +/- 13.9%, 12.7%, and 8.3%, .

Aim 2: we will measure inpatient utilization, emergency room utilization and QoL of patients receiving telehealth technology vs. standard of care patients.

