Statistical Methods: ER *Utilization*: The statistical methods for analyzing ER utilization outcomes will be similar to those presented for inpatient utilization. Specifically, for outcome 2b.1, the proportions of patients in each group who utilized the ER will be compared using the standard Chi-square or Fisher's exact test. Associated 95% confidence intervals for these proportions and their differences will be computed using exact methods. For outcome 2b.2, (overdispersed) Poisson regression will be used. For outcome 2b.2, Lachenbruch's two stage procedure for zero-inflated data will also be considered.²⁵

Sample Size Considerations. The sample size and power considerations identified for outcomes 2a.1 and 2a.2 are virtually identical for ER utilization.

2c. Quality of Life assessment: We will use the Minnesota Living with Heart Failure Questionnaire²⁷ (Appendix 4) to assess patient QoL (QoL). While HF will continue to impact the lives of these patients, it is reasonable to believe that proper disease management via telehealth will improve QoL due to earlier exacerbation detection and lowered hospital utilization. We will compare questionnaire results between patients receiving TSM and usual care patients. Measures of QoL are defined as the 3 month QoL score minus the 1 month QOL score, where a positive score indicates a worsening of QoL .

Statistical Methods. A two-sample z-test will be used to compare changes in QoL between groups.

Sample size and power considerations. we expect to enroll 52 patients in each group, a 2-sample z test (80% power) to detect an effect size of 0.39 or greater, which is considered "small" to "medium".²⁸

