ED utilization was defined as whether or not an individual patient had at least one ED visit over the 90-day period. Binary outcomes for ED visits and hospitalizations were analyzed using the standard Chi-square or Fisher's exact test. Associated 95% confidence intervals for these proportions and their differences were computed using exact methods. The number of ED visits as well as hospitalizations within each group were separately compared using Poisson regression (SAS PROC GENMOD). Due to excess zeros (i.e., zero inflation), methods for over dispersed Poisson were required for both ED visits and hospitalizations. Cumulative LOS (inpatient days) was analyzed using a negative binomial regression. HF-related hospitalizations, ED visits, and LOS were analyzed in the same fashion described above, as were cardiovascular related outcomes. Reasons for ED visits as well as hospitalizations were classified as: HF alone (yes/no), cardiovascular related alone (yes/no), or both by the clinical team.

Repeated measures analysis of variance (RMANOVA) with a mixed models approach was used to compare changes at enrollment and at 90 days between groups. New York Heart Association (NYHA) class, PHQ-4, MLHFQ Physical and Emotional subscales were also analyzed using RMANOVA. The subscales of Anxiety and Depression, as measured by the PHQ-4, were dichotomized to presence or absence and Generalized Estimating Equations (GEE) were used to analyze these binary data. Days at home was

calculated as a proportion of days spent out of hospital during the 90 day period. The two groups were compared using the Mann-Whitney test.

Subgroup analyses included: patients hospitalized, heart class (2 vs. 3), and patients not receiving home care (prevalent in disparity populations). For the TSM group only, adherence was calculated, with low adherence defined as less than 10 vital signs uploads over the 90 day period.

Sample size and power calculations were based on previous literature and preliminary data from a non-disparity randomized RCT TSM study. We hypothesized that 75% of patients in the COM group would be hospitalized at least once during the study period and that TSM would reduce that rate to 50% (a relative reduction of 50%). The calculation was based on a chi-square test (alpha=0.05, two-tailed) with an n=52 patients per group. All analyses were performed using SAS 9.4 (SAS Institute Inc., Cary, NC).

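### The quality-of-life power statement is wrong: 52 per group gives 80% power for an effect size of 0.55, not 0.39, and only about 51% power at 0.39

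*Protocol*

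**What the plan says.** Protocol section 2c (Quality of Life assessment) fixes the outcome, the test and the power claim:

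- Outcome: "Measures of QoL are defined as the 3 month QoL score minus the 1 month QOL score".
- Test: "A two-sample z-test will be used to compare changes in QoL between groups".
- Power: "we expect to enroll 52 patients in each group, a 2-sample z test (80% power) to detect an effect size of 0.39 or greater". The Protocol describes an effect of this size as lying between small and medium, citing a reference.

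The group size agrees with the design description under Aim 2: "This is a prospective randomized controlled trial of 104 community-dwelling patients", that is, two groups of 52. The Aim 1 sample size paragraph gives 116 randomised, 58 per arm, to leave 52 in the telehealth arm.

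Section 2c states no alpha, sidedness, standard deviation or correlation. The only alpha in either document is in the SAP, for hospitalisation: "The calculation was based on a chi-square test (alpha=0.05, two-tailed) with an n=52 patients per group". The SAP has no power statement for QoL, so 0.39 is the only such figure and nothing corrects it.

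**The concern.** The test, the group size and the power are all given, so the detectable effect can be checked directly. A standardised difference of 0.39 is too small for two groups of 52 at any usual significance level.

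The hypothesis in the Protocol's objectives section has two parts, better QoL and lower hospital use, and QoL is also part of Aim 2. If the power claim is taken at face value, a non-significant QoL comparison looks like fair evidence against an effect of 0.39 or more. In fact the trial would miss a true effect of 0.39 about half the time.

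**Working it through.** **Inputs**

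- n = 52 per group, power 80%, effect size 0.39, two-sample z-test: Protocol section 2c.
- Alpha 0.05 two-sided: an assumption, borrowed from the SAP's hospitalisation calculation. Alternatives are shown below.
- The effect size is the difference in mean change divided by the SD of the change score, because the change score is the defined outcome.

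**Where 0.39 comes from**

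z(0.975) + z(0.80) = 1.960 + 0.842 = 2.8016.

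- One-sample formula, n = 52: 2.8016/√52 = 0.3885.
- Two-sample formula, 104 per group: 2.8016 × √(2/104) = 0.3885.

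Both round to the stated 0.39. Neither describes two groups of 52.

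**Detectable effect for the stated design**

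d = 2.8016 × √(2/52) = 2.8016 × 0.1961 = 0.549.

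This is 0.549/0.39 = 1.41 times the stated value, or 41% larger. A t-test gives 0.555.

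**Power at 0.39**

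Power = Φ(0.39/0.1961 − 1.960) = Φ(1.989 − 1.960) = Φ(0.029) = 0.511. A t-test gives 0.504.

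The two-sided significance threshold is 1.960 × 0.1961 = 0.384 SD. A true effect of 0.39 lies almost on that threshold, which is why power is close to one half.

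**Sample size needed for 0.39**

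n = 2 × (2.8016/0.39)² = 103.2, so 104 per group (208 in total).

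**Other readings**

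| n per group | Alpha | Detectable effect, 80% power | Power at 0.39 |
|---|---|---|---|
| 52 | 0.05 two-sided | 0.549 | 51.1% |
| 58 | 0.05 two-sided | 0.520 | 55.6% |
| 52 | 0.05 one-sided | 0.488 | 63.5% |
| 58 | 0.05 one-sided | 0.462 | 67.6% |
| 52 | 0.10 one-sided | 0.416 | 76.0% |
| 58 | 0.10 one-sided | 0.394 | 79.4% |

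With 52 per group, 80% power at 0.39 requires a critical value of 1.989 − 0.842 = 1.147, a two-sided alpha of about 0.25. The last row comes close to 0.39, but it needs both an alpha that appears nowhere in the documents and a group size that section 2c does not use.

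**Effect size scaled to the raw-score SD**

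The SD of a change score is √(2(1 − ρ)) times the raw SD, where ρ is the correlation between the two assessments. For 0.39 raw SDs to equal 0.549 change SDs, √(2(1 − ρ)) must be 0.39/0.549 = 0.710, so ρ ≈ 0.75. With baseline adjustment (ANCOVA) instead, ρ would be about 0.70. The documents give no correlation, and section 2c tests the change score without adjustment.

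**The case against.** The arithmetic is not open to serious dispute. The case on the other side concerns weight and wording.

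- **QoL is not labelled primary.** Protocol Table 1 gives that label to emergency room use and hospitalisations, and the SAP bases sample size on hospitalisation. This stands: the error leaves the primary power calculation untouched, and 0.39 does not appear to have set the sample size. QoL is nevertheless part of the stated hypothesis.
- **It is too late to alter the design.** The Protocol's recruitment section says enrolment to the telehealth arm has closed, and the SAP is written in the past tense. This also stands. What remains is a correction to the record; no estimate, test or interval changes.
- **A null result is judged from its confidence interval, not from planned power.** This is right in principle, and neither document says how it would read a null result. The risk is that readers rely on the power claim, not that the plan commits itself to a wrong inference.
- **Alpha is not stated for QoL.** True. Across two-sided and one-sided 5% tests with 52 per group, the detectable effect runs from 0.49 to 0.55 and power at 0.39 from 51% to 63%. The stated claim fails throughout that range.
- **The cause is inferred.** Also true. A dropped factor of √2 and the trial total of 104 entered as the group size give the same number, and the documents do not show which occurred.
- **The SAP uses a different analysis.** It compares enrolment and 90 days by repeated-measures mixed models. With complete data at two time points, the group comparison is essentially one of change scores, so this does not rescue 0.39.

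**Conclusion.** The concern holds. With 52 per group, the two-sample z-test has 80% power for an effect size of 0.55, not 0.39, and power of about 51% at 0.39. The detectable effect is understated by a factor of about √2, and the sample size needed for 0.39 is twice the plan.

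The figures 0.55 and 51% rest on a two-sided alpha of 0.05, borrowed from the SAP, and on an effect size in SDs of the change score. The conclusion that 0.39 is wrong does not depend on the sidedness of a 5% test or on counting all 58 randomised per arm. The origin of the error is likely but unproven. Its consequence is limited to what can be claimed about QoL.

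**What to change.** Replace the power sentence in Protocol section 2c with one to this effect: with 52 patients per group and a two-sided alpha of 0.05, a two-sample z-test of the change in QoL has 80% power to detect a difference of 0.55 SD of the change score, and about 51% power at 0.39 SD.

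Along with it:

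- State the alpha and the SD to which the effect size refers. If a raw-score SD was intended, give the assumed correlation and its source.
- Recheck the small-to-medium description against the cited reference for 0.55, or remove it.
- Say which QoL analysis the statement applies to, since the SAP uses a repeated-measures model from enrolment to 90 days in place of the z-test on months 1 and 3.
- Report the QoL difference with its 95% confidence interval, and do not present a non-significant result as excluding an effect of 0.39.

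The cost is a few lines of text and a less favourable power figure. Enrolment and study procedures do not change.

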2a. Measures of Inpatient Utilization. Inpatient utilization will be measured in three ways, including: 2a.1) whether an individual subject had at least one inpatient hospitalization over the 3 month period; 2a.2) the number of hospitalizations experienced by an individual subject over the 3 month period; and 2a.3) cumulative length of stay (LOS) (inpatient days) experienced by an individual subject over the 3 month period (i.e., for multiple hospitalizations, the sum of all LOS's will be computed as the cumulative LOS). Cumulative LOS will be analyzed in two ways: intention to treat (ITT) analysis, and for only those hospitalized. The ITT analysis will include all patients, regardless of hospitalization history, to address the bigger public health issue: does TSM have an impact on LOS overall? A secondary analysis will look at LOS only for those who experienced a hospitalization. Finally, after ITT analysis, secondary analyses will include covariate adjustments for possible confounders.

Statistical Methods: Inpatient Utilization. For outcome 2a.1, the proportions of patients in each group who were hospitalized will be compared using the standard Chi-square or Fisher's exact test. Associated 95% confidence intervals for these proportions and their differences will be computed using exact methods. For outcome 2a.2, the number of hospitalizations will be compared using Poisson regression (SAS PROC GENMOD). It is likely that, due to excess zeros (i.e., zero inflation), methods for overdispersed Poisson will be required. Another approach for both outcomes 2a.2 and 2a.3 will be to use Lachenbruch's two stage procedure for zero-inflated data.30 For these primary ITT analyses, no adjustments will be made for any covariates.

Sample size considerations: We expect to enroll 52 patients in the TSM group which will yield the necessary statistical power.

2b. Measures of ER Utilization, defined as: 2b.1) whether or not an individual subject had at least one ER visit over the 3 month period; and 2b.2) the number of ER visits experienced by an individual subject over the 3 month period. Covariate adjustments will be made for potential confounders.

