Secondary Analyses: Adjusting for Confounders: Potential confounders will be demographic (age, gender, race, ethnicity, primary language spoken, insurance status (insured vs notinsured), education (high school graduate vs. non-graduate), major co-morbidities (e.g., diabetes Y/N) and functional variables (e.g., heart class, depression symptoms, anxiety symptoms, and caregiver support). All of these measures will be assessed at baseline only. We will use the PHQ4¹⁹ (Appendix 5) to assess symptoms of depression and generalized anxiety disorder as both of these are factors known to have direct impact on cardiovascular outcomes.²⁹ This is a brief measure (with limited potential participant burden) that has been validated and widely used with heart failure patients.^{30,31} It has also been translated into Spanish.^{32,33} We will also use a brief measure of caregiver support that assesses assistance with heart failure medical care. The stem question asks if there is someone in participants' lives who helps with heart failure medical care and if answered in the affirmative, participants then indicate their relationship with that person and whether the person lives in the home (Appendix 6). To this end, multiple logistic regression will be used where the outcome variable is hospitalization (yes/no) and the predictor variables are treatment group (telehealth vs. control) on the aforementioned covariates. For number of hospitalizations and length of stay (LOS), analysis of covariance (ANCOVA) will be used if the required distributional assumptions can be met. If not, extension of Lachenbruch's procedure using logistic regression and analysis of variance will be used.

CONFIDENTIALITY

Confidentiality will be protected by assigning to each subject a research data a unique identifier known only to IRB approved personnel.

Storing Documents in Hard Copy

Any documents that contain PHI (e.g., consent forms, link between the ID to subjects' identifiers) will be stored in a locked cabinet within the office of the principal investigator, separately from any de-identified research documents. IRB approved personnel will be the only individuals with access to any research documents containing PHI.

Storing Documents Electronically

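### The secondary adjusted hospitalization model has about 3 non-hospitalized patients per term; if TSM works, its log odds ratio is exaggerated by roughly 17–27% and its interval under-covers

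*Protocol*

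**What the plan says.** The Protocol, under *Secondary Analyses: Adjusting for Confounders*, plans an ordinary logistic model of any hospitalization: "multiple logistic regression will be used where the outcome variable is hospitalization (yes/no) and the predictor variables are treatment group (telehealth vs. control"), together with the covariates named just before. Those are age, gender, race, ethnicity, primary language, insurance, education, major comorbidities (diabetes as the example), heart class, depression symptoms, anxiety symptoms and caregiver support. The comorbidity and functional lists are given as examples, so more could be added. No selection step, limit on terms or penalization is stated.

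The event rates come from the SAP's sample-size paragraph: "We hypothesized that 75% of patients in the COM group would be hospitalized at least once during the study period", and "TSM would reduce that rate to 50% (a relative reduction of 50"%. It adds: "The calculation was based on a chi-square test (alpha=0.05, two-tailed) with an n=52 patients per group". The Protocol's Aim 1 sample-size text gives a larger number randomized: "We will randomize 116 patients as they are discharged from the hospital (58 per arm").

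The Protocol's statistical methods for inpatient utilization leave the primary intention-to-treat analyses unadjusted. The SAP lists chi-square or Fisher tests for the binary outcomes and describes no covariate-adjusted hospitalization model.

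**The concern.** Maximum-likelihood logistic regression is not unbiased in small samples. When the less frequent outcome supplies only a few patients per fitted term, estimated log odds ratios move away from zero and the model's standard errors understate the true spread. The planned model has more terms than the expected number of non-hospitalized patients supports.

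The adjusted odds ratio will be read beside the unadjusted one. If TSM is protective, the adjusted value will on average lie further below 1 than it should. A reader could credit the difference to control of confounding when part of it is small-sample bias. The reported interval would also claim more precision than the model delivers.

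**Working it through.** **1. The plan's own figure.** The SAP gives 52 per group for 75% against 50%, two-sided alpha 0.05, but no power for this endpoint; the Protocol says only "We expect to enroll 52 patients in the TSM group which will yield the necessary statistical power". The 52 therefore cannot be reproduced as such. With the pooled normal approximation, 52 per arm gives 75.7% power and 58 per arm gives 80.2%. The SAP calls the contrast a 50% relative reduction, but (75 − 50)/75 = 33%. I use the two stated rates, which give an odds ratio of (0.50/0.50)/(0.75/0.25) = 0.333.

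**2. Size of the limiting outcome group.**
- 52 per arm: 52 × 0.25 + 52 × 0.50 = 13 + 26 = 39 not hospitalized, and 104 − 39 = 65 hospitalized. Non-hospitalized is the smaller group.
- 58 per arm: 14.5 + 29 = 43.5 not hospitalized.

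**3. Terms.** Treatment plus 12 covariates at one degree of freedom each is 13. NYHA class 1–3 entered as a three-level factor makes 14.

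**4. Patients per term.**
- 39/13 = 3.0 and 39/14 = 2.8.
- 43.5/13 = 3.3 and 43.5/14 = 3.1.
- Whatever the rates turn out to be, the smaller group cannot exceed half the sample: at most 52/13 = 4.0 with 104 patients, or 58/13 = 4.5 with 116.

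**5. Consequence when the effect is real.** Trials were simulated at 75% against 50% and the full model fitted by maximum likelihood (6,000 trials per scenario at 52 per arm). Covariate prevalences and effects are not in the documents and are assumed. Exaggeration is measured against the true *conditional* log odds ratio, because an adjusted odds ratio legitimately differs from the unadjusted one. With moderate covariate effects the true values are −1.174 conditional and −1.099 unadjusted.

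| Scenario | Log-OR too large by | Mean model SE | Actual SD | SE too small by | 95% CI coverage |
|---|---|---|---|---|---|
| 13 terms, moderate effects | 21% | 0.536 | 0.604 | 11% | 92.7% |
| 14 terms, no covariate effects | 21% | 0.512 | 0.574 | 11% | 92.6% |
| 14 terms, moderate effects | 22% | 0.540 | 0.610 | 11% | 92.0% |
| 14 terms, strong effects | 27% | 0.619 | 0.738 | 16% | 91.5% |
| 14 terms, Gaussian covariates | 22% | 0.555 | 0.624 | 11% | 92.3% |
| 14 terms, moderate effects, 58 per arm | 18% | 0.497 | 0.556 | 11% | 92.4% |

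In the first row the true log-OR is −1.188 and the mean estimate −1.433; −1.433/−1.188 = 1.21. On the odds-ratio scale, 0.305 is estimated on average as 0.238. Simulations with other assumed covariates (13 terms, 52 or 58 per arm) gave milder figures: 17–20% exaggeration, standard errors 7–12% too small, coverage 92–94%. If the open-ended lists took the model to 18 terms, exaggeration was 31% and coverage 90.1%.

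**6. Consequence under the null.** With the same rate in both arms and 14 terms, the average odds ratio was about 1.01, coverage 93.8% and type I error 6.2%. An unadjusted logistic fit to the same data rejected in 5.2–5.5% of trials.

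**7. Effect of the alternatives** (52 per arm, moderate effects, true conditional log-OR −1.174).
- Firth's fit of the full list: mean −1.20, SE 0.505 against SD 0.481, coverage 96.7%.
- Treatment, gender and class 3 only (39/3 = 13 per term): mean −1.18, SE and SD both 0.446, coverage 95.6%.
- In a separate simulation with true log-OR −1.10, treatment plus three covariates (39/4 = 9.75 per term) gave a mean of −1.13, while the full maximum-likelihood model gave −1.33.

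**The case against.** The strongest objection is reach. This is a secondary Protocol analysis that the SAP does not carry forward, and the primary comparison uses no covariates. That stands: nothing here touches the trial's main result. It does not settle the matter, because the SAP does not withdraw the Protocol's model either.

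A reader might infer that the adjusted model would make an ineffective intervention look effective, or rescue a failed primary test. The documents and calculations do not support this. With no true effect there is no bias. In 4,000 simulated trials per scenario at the planned rates, the adjusted model turned a non-significant chi-square result significant in 3.6% (no covariate effects) or 6.4% (log-OR 0.4 each) of trials. It turned a significant result non-significant in 5.6% or 5.9%. Under the null the first kind of reversal (2.5–3.3%) exceeded the second (1.5–2.1%) by only about one percentage point.

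A reader might also take the interval to be narrower than the unadjusted one. It is not: on the log scale it is 19–44% wider. It is too narrow only relative to the adjusted estimate's own sampling variability.

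Two further points stand. Fourteen terms requires heart class at three levels, whereas the SAP's subgroup analysis compares class 2 with class 3, so 13 is equally defensible; the conclusion is the same. And non-convergence or separation should not be pressed: at the planned rates it ranged from 0 to 4% of fits, depending on covariate prevalences that the documents do not give.

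**Conclusion.** The concern holds as a modest, cheaply removed flaw in a secondary analysis. At about 3 non-hospitalized patients per term (2.8–3.3 across the defensible counts), a real TSM effect would be reported with a log odds ratio about 17–27% too far from zero. Because TSM is expected to protect, the odds ratio would be pushed lower. Standard errors would be about 7–16% too small and 95% coverage about 92–94%. If TSM has no effect, the estimate is unbiased and type I error is about 5–7%.

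The patient counts rest on the SAP's planning rates and on 104 to 116 patients analyzed. The bias and coverage figures rest on assumed covariate distributions. The exaggeration does not depend on the covariates being prognostic, since it was 21% when they had no effect at all.

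**What to change.** First state whether the adjusted hospitalization model is still planned, since the Protocol has it and the SAP does not describe it. If it is kept, choose one of these:

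- **Firth's penalized likelihood on the full listed set**, using the FIRTH option in PROC LOGISTIC with profile penalized-likelihood intervals. This keeps every covariate and needs only options in the SAS call. The cost is slightly conservative coverage, about 96–97%.
- **A shorter model**: treatment, heart class, gender and age, with the full list as an exploratory check. Heart class is a balancing factor in both documents; gender is named as one only in the Protocol's *Recruitment Procedures*, and the SAP stratifies by heart class alone. The cost is that fewer covariates are adjusted for.

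Either way, fix the covariate list and the coding of heart class in advance, so that the open-ended examples cannot add terms. Apply the same choice to any adjusted yes/no model for ER visits.
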